4.4 Study outcomes/endpoints

The primary aim of this study is adherence, as assessed using daily diaries. How many days the participants were able to restrict their eating to the 10-h window will serve as the primary endpoint. The daily diary will include the time of the first calorie consumed and the time of the last calorie consumed every day for the 14-day intervention. Success will be defined by the participants reaching the fasting target at least 11 of the 14 days on average. This goal is reasonable based on a study by Kesztyüs et al.,²¹ whose participants adhered to this dietary pattern $85.5 \pm 15.2\%$ of days over a three-month intervention, and a study by Gabel et al.,¹⁷ whose participants adhered 5.6 ± 0.3 days/week (80%) for 12 weeks on average.

A secondary aim is retention; it is expected that at least 80% (32 out of 40) of those who provide baseline data also provide post-intervention data.

Another secondary aim will be safety. We hypothesize that body weight will be maintained within 5% of baseline throughout the intervention and that there will be no adverse events that are Grade 2 or worse that are attributable to the intervention.² To ensure safety in regard to weight loss, body weight will be measured three times: baseline (Day 1), mid-point (Day 8), and post-intervention (Day 15). Body weight will be measured by the participant by a scale that is provided, and then reported on the daily diary (e.g., BalanceFrom Digital Body Weight Bathroom Scale). To ensure consistent and reliable measures, participants will be asked to weigh themselves in the morning, before eating or drinking, with minimal clothing. The scale should be placed on a hard, level surface (e.g., tile, wood) that is the same for each measurement, if possible, because there can be slight variations in measurements if the scale is placed on a rug vs. a hardwood floor, for example. Participants will have the option of keeping the scale at the end of the study.

To ensure safety in regard to adverse events, we will closely monitor all adverse events as described by the CTCAE, version 5.² Adverse events that will be of particular interest due to potential causality include weight loss or weight gain (see §9.1.1), dizziness, and exacerbation of fatigue.

Also, to ensure safety in regard to caloric intake, participants will complete a 24-h Food Record before the intervention (their normal diet and dietary pattern). This will be done prospectively on any day before they begin the TRE intervention. The 24-h Food Record entails noting the identity of the food, the quantity, and the time it was ingested. They will also complete a prospective 24-h Food Record, including times, on Day 14, the last day of the intervention. The Food Record will be analyzed for total calories, macronutrients, micronutrients, and bioactive compounds using Nutrition Data System for Research (NDSR; Regents of the University of Minnesota, Minneapolis, MN) or a similar program.

An exploratory aim of this study is cancer-related fatigue, as assessed using the FACIT-F, BFI, and Symptom Inventory. Patients will complete these instruments at baseline and post-intervention.

1. Functional Assessment of Chronic Illness-Fatigue (FACIT-F) questionnaire: The FACIT-F is a 40-item, validated, commonly used measure of fatigue that is comprised of five subscales: physical well-being, social well-being, emotional well-being, functional well-being, and fatigue.²² It captures symptoms in these categories over the last 7 days.
2. Brief Fatigue Inventory (BFI): The BFI is a 10-item fatigue questionnaire that is also validated and commonly used.²³ It captures fatigue *now* and the usual and worst in the last 24 h. It also includes 6 single-item questions regarding how fatigue has interfered with general activity, mood, work, etc.
3. Symptom Inventory (SI): The symptom inventory (modified from the MD Anderson Symptom Inventory²⁴) includes 19 items that are common in the cancer experience (e.g., pain, distress, lack of appetite, numbness and tingling, fatigue), as well as 8 items related to how much these symptoms interfere with activities of daily living and quality of life. As many symptoms often correlate with each other including fatigue (i.e., symptom clustering²⁵), it is important to capture the change in many symptoms from baseline to post-intervention. Exploratory analyses will probe whether adherence to the diet or high consumption of any dietary component correlates with the change in any of these symptoms over the two-week intervention.

There are a total of six questionnaires and survey assessments that will be completed. The on-study form will be completed at baseline only; the daily diary will be completed during the intervention; the others will be completed at baseline and post-intervention:

- On study (demographics and clinical characteristics; baseline only)
- FACIT-F (Fatigue and quality of life)
- BFI (fatigue)
- Symptom inventory
- 24-h Food Record
- Daily diary

The 3-4 questionnaires that will be completed at baseline and post-intervention should take approximately 10 min in total to complete. The daily diary will take less than 1 min to complete each day. The 24-h Food Record will require noting the time, identity, and quantity of food eaten throughout one day.

4.5 Timeline

Upon opening of the study, we expect that approximately 4-8 participants will be recruited per month for approximately 8 months. Data will be entered as they come in, and data analysis will take place soon thereafter. These data will be used to inform a follow-on randomized clinical trial for which a grant

will be submitted in the Summer 2020.¹ It is also anticipated that one manuscript will also emerge from this study, which will be submitted for publication within one year of the study closing.

4.6 Design considerations

Why a 10-hr TRE pattern? Intermittent fasting has gained a lot of interest in the last decade due to its strong pre-clinical data supporting its ability to regulate circadian rhythm, improve homeostatic metabolism, and alleviate age-related morbidities.¹⁴ The investigators and the NCI believe that it will be a promising lifestyle intervention to alleviate symptoms of cancer and side effects of treatment.¹ Intermittent fasting protocols include more extreme patterns (e.g., alternate day fasting,²⁶ as well as TRE with shorter time windows, such as 4-h²⁷). However, most human studies thus far have been performed among healthy participants, and especially participants who are overweight. It is hypothesized that 10 hours is the longest window that can be implemented that will be safe, effective, and not too uncomfortable for the participants. With a 10-h window, none of the three traditional meals (e.g., breakfast, lunch, dinner) have to be “skipped,” though meals might need to be shifted. The primary goal is for the diet pattern in this line of research is to regulate circadian rhythm, not induce caloric restriction.

Why in survivorship vs. during adjuvant treatment? Participants will be recruited 4 months–5 years after chemotherapy, surgery, and/or radiation for curative intent. Thus, their immediate, acute side effects of treatment will have subsided though persistent side effects will still be present. It is thought that survivors will have enough physical and mental resources to adhere to a change in diet pattern, while patients actively undergoing treatment will have a much harder time.

Why a 14-day duration? Studies that have implemented TRE interventions have used a wide range of intervention lengths, from 4 days¹⁸ to 12 weeks.¹⁷ The 4-day intervention had a positive effect on 24-hour circulating glucose concentrations, lipid metabolism, and circadian rhythm clock gene expression.¹⁸ Other nutrition interventions, such as a Mediterranean Diet, have shown measurable effects on vigor (similar to fatigue) in 10 days.²⁸ The main outcome herein is feasibility to recruit and retain participants, and it is thought that 14 days is an appropriate amount of time to know if someone will be willing to adhere to a short-term lifestyle change. Two weeks includes two full weeks including weekends, and is thus better than 10 days so that the presence (or absence) of weekend social activities during the intervention is not a biasing factor.

Should we directly monitor glycemia? It is possible that this intervention could lead to hypoglycemia among individuals who are at risk due to the presence of type 1 diabetes mellitus and, especially, use of insulin therapy.²⁹ However, specific research addressing this question has shown that various regimens of TRE and intermittent fasting *do not* lead to hypoglycemic events in the vast majority of individuals studied, including those with type 2 diabetes.^{30,31} In fact, TRE shows glycemic benefits for individuals with prediabetes³² as well as overweight individuals.¹⁸ Specifically, Singh et al. recruited 32 patients with a high risk of cardiovascular disease (nine with type 2 diabetes); participants consumed the vast majority of their calories in the evening (a calorie restrictive protocol that is more extreme than the one proposed herein) including no breakfast and there were no hypoglycemic episodes.³⁰ In addition, Arnason et al. encouraged 10 patients with type 2 diabetes who were taking metformin consume all their food within a 4-6 hour eating window (shorter than the proposed 10-hour window); they observed zero instances of hypoglycemia and concluded that the regimen was safe for this population.³¹ Thus, we are excluding individuals on insulin therapy, and we will require approval from each potential participant’s oncologist. In the sign-off form, we will emphasize that he or she should reach out to the primary care provider to ensure that the patient is not in this “high risk” group.

5. Inclusion and exclusion criteria

Participants will be selected to represent a broad range of patients with varying demographics, incoming metabolic functioning, and clinical cancer characteristics. This study will not be powered for any subgroup analyses.

Inclusion criteria (Participants must...):

1. Have completed adjuvant chemotherapy, surgery, and/or radiation for cancer at least 4 months and not more than 5 years prior to enrolling,
2. Have a baseline level of fatigue, as determined by reporting a score of 3 or higher for the question, “In the last week, how bad was your worst fatigue on a scale from 0-10?”
3. Be able to speak English,
4. Be at least 18 years old,
5. Be willing and able to adhere to study procedures, and
6. Be able to provide informed consent.

Exclusion criteria (Participants must not...):

1. Already eat all their food within a window that is 10 h or shorter most (6/7) days of the week,
2. Be underweight, as defined as a body mass index $\leq 20.0 \text{ kg/m}^2$,
3. Not have surgery planned in the next month,
4. Not have any contraindications to the proposed nutrition intervention as identified by their medical provider, their designee, or the study team (e.g., type 1 diabetes, risk for hypoglycemia, medication requirements, pregnancy, breastfeeding,³³ recent history of an eating disorder),
5. Not be taking insulin, or
6. Be on enteral or parenteral nutrition.

Cancer survivors may be taking hormone therapy, immune targeted therapy (e.g., Herceptin), or another type of therapy to prevent recurrence.

6. Recruitment methods

6.1 Identification and recruitment

[name] or a member of the study team will recruit participants using the Cancer Control group's established procedures. Before recruitment approval will be obtained by the James P. Wilmot Cancer Institute Clinical Trials Peer Review and Monitoring Committee (PRMC) as well as the University of Rochester Medical Center (URMC) Research Subject Review Board (RSRB). Potential participants will be identified using three methods: (1) screening medical records, (2) direct referral from providers (e.g., nurses and physicians), and (3) flyers.

6.1.1 Identification and recruitment via medical records

Potentially eligible participants receiving care at the URMC will be identified in a HIPAA-compliant manner by study personnel via review of scheduled outpatient appointments. The study team will then review any potential candidates. Medical records typically show time since completion of adjuvant

therapy (e.g., surgery, chemotherapy). If an individual appears to be eligible, the study team will contact the treating provider (or a designee) to notify them of a potential candidate and obtain approval to speak with the patient. The provider (or a designee) will approach the potential participant at a regularly scheduled oncology appointment. This initial contact will assess whether the participant has any interest in participating in a clinical trial to investigate the feasibility to implement a TRE dietary intervention. If the person is interested, the provider will refer the individual to the study team. The study team will then meet with the candidate in a private room to discuss the study activities in detail and review eligibility (either that day or at a later date). If the person is eligible, study personnel will explain the details of the study. Study personnel can obtain informed consent right then or at a later date from those who agree to participate. After consent is provided, the participant will be provided with study materials.

6.1.2 Identification and recruitment via direct referral from physicians, physician assistants, and nurses

The study team is working with several oncologists (including, but not limited to the medical monitor [name]) and his medical team (e.g., nurses, physician assistants) to identify potential patients at the University of Rochester who are likely eligible for our study. If the patient is eligible based on information in the medical records and from the physician and medical team, the provider will be asked to refer the person to the study team (or obtain the physician's permission to contact the person) to discuss this study.

6.1.3 Flyers

A flyer advertising our study will be placed in locations designated for such use. Cancer survivors can contact a member of the study team directly for more information. Their medical provider will be contacted to ensure that the intervention is appropriate for the potential participant before consenting them.

6.2 Screening

For convenience to the potential participant, the person's clinic appointment might be combined with their screening and consent, or participants can undergo the screening and consent process remotely via eConsent. To protect the privacy of potential participants, face-to-face recruitment discussions will be conducted in a private location.

[name] or a member of the study team will meet the potential participant in person or talk to them over the phone to explain the project and invite them to participate. It is expected that some patients will decline to participate, and some will not be eligible;¹³ approaching the same individual twice will be avoided by keeping a screening log containing the following information:

- Screening ID (1, 2, 3,...)
- Name
- Date of contact
- Medical record number
- Where/how we talked to the potential participant (e.g., clinic location, phone)
- Whether the patient was eligible or not
- If ineligible, the reason they are ineligible
- Whether the patient ultimately consented or declined
- If declined consent, the reason for declining consent

- If consented, the participant ID in the study (e.g., 101, 102, 103, ...)

Patients will need medical clearance from their provider to participate in the study.

7. Consent process

7.1 Written consent

For participants who are interested in participating, a member of the study team will meet with the potential participant in a private room. She or he will go through the consent form with the patient face-to-face to ensure comprehension. They will then be given the option to sign the consent form. [name] (study chair) will be available to answer any questions the potential participant may have about any aspect of the study prior to consenting and throughout the entire study period. The participants will also have access to the dietitians at the Integrative Oncology and Wellness Center at Pluta Cancer Center (e.g., [name], RD) if they have other diet-related questions. Potential participants will be allowed to take the consent form home to think about and discuss with family or friends; each potential participant will have sufficient time to consider participation. To minimize coercion, the study team will emphasize that participation is completely voluntary and their cancer care will not be affected by their participation in the study.

7.2 eConsent

In lieu of the paper-based consent document, consent may occur remotely using the RSRB-approved eConsent document provided via REDCap. The study staff will screen for potential participants using the above screening procedures and initiate initial contact via the following methods: 1) the treating oncologist or a member of the medical team (e.g., nurse practitioner) will introduce the study to the participant via a clinic appointment (in person or telehealth) and inquire if it would be okay for our study team to contact them, 2) with approval of the treating oncologist or a designee, a recruitment letter will be mailed to the potential participant briefly describing the study and asking them to contact us if they would like more information, and 3) with approval of the treating oncologist or a designee, a message will be sent to the potential participant via eRecord (myChart) briefly describing the study and asking them to contact us if they would like more information. If a potential participant is interested, the study team will talk to the person on the phone and obtain verbal permission from the patient to send a copy of the eConsent via email or text message stating, “Because URMC can’t control the security of email or text messages once we send them, we need your permission to text or email you. Do you want to receive a copy of the consent document and a link to the eConsent via text or email?” Verbal permission from the patient will be documented. We will email or text the eConsent in the form of a pdf document and set up a phone call or Zoom meeting (participant’s choice) to formally go over the consent document. In a separate email or text, we will provide a link to the eConsent document as well as instructions on how to access the eConsent—we will use verification with a passcode based on known information (e.g., the patient’s home zip code). No personal health information will be sent via any emails/texts. The eConsent documents may be viewed on computers, electronic tablets, or smartphones. The pdf copy of the eConsent and the REDCap eConsent will have identical information; it will be optional for the person to review the consent before the study team discusses it with them. After a member of the study team reviews the consent document with the participant over the phone or computer, they will have the opportunity to electronically sign the eConsent via REDCap. The person obtaining consent will initiate the eConsent process from within REDCap for their name and a timestamp to appear on the study participant’s signed consent form. In order to authenticate that the person signing is that person, we will again use a passcode based on known information (e.g., the patient’s year of birth). Once the eConsent form is signed and submitted, the patient and/or legally

authorized representative will be able to receive a print out of the paper copy, download a pdf, and/or receive an email with a PDF attachment of the signed consent form.

8.1 Overview of study

This study is a single-arm feasibility TRE intervention for 14 days, during which participants will be asked to consume all of their calories within a 10-h window. The primary goals are to assess the feasibility of implementing the intervention and participants’ adherence to the dietary pattern over the 14 days. Information on fatigue and quality of life will also be collected; while large changes in these measures are not expected, it will be ensured that the diet pattern does not cause large amounts of fatigue, a large

reduction in quality of life, or exacerbation of any chronic symptoms. It is hypothesized that a longer duration intervention (e.g., at least 4-12 weeks³⁴) will reduce cancer-related fatigue and other symptoms.

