4.3 Study interventions

This will be a single-arm, feasibility pilot study that recruits 40 cancer survivors. After screening and consent, participants will complete an on-study form and baseline questionnaires: the Functional Assessment of Chronic Illness Therapy (FACIT-F), Brief Fatigue Inventory (BFI), the 27-item modified MD Anderson Symptom Inventory, and a 24-h Estimated Food Record. These questionnaires can be completed either online via REDCap or on paper (participant's choice) and take less than 10 min total to complete. Participants will be provided with a small bathroom scale, with which they will be asked to report their weight at baseline (Day 1), mid-point (Day 8), and post-intervention (Day 15). We prefer that body weight is measured at home, in the morning, before food or drink is ingested, without clothing. Before the intervention period, all participants will be instructed as to how to follow a TRE diet pattern. The TRE window will be 10 hours long and will be selected by the participant based on their normal meal patterns and preferences. For example, the window could be 7am-5pm, 8:30am-6:30pm, or 12:00pm-10:00pm. However, the window should not change during the intervention period. Every day for 14 days, participants will be asked to consume food and beverages only within the 10-h window; water will be allowable any time. Because of the potential of caffeine and artificial sweeteners to affect circadian rhythm,^{19,20} coffee, tea, chewing gum, and diet beverages will be discouraged during the fasting window. Also for these 14 days, participants will complete a daily diary at the end of the day noting the time they wake up, the time

of their first calorie, the time of their last calorie, the time they go to bed, and their average fatigue level for the day.

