8.2.5 Schedule of assessments

After consenting to the study, the participant can decide to start the intervention any day within the next week. Preferably, the 24-h Food Record and baseline questionnaires will be performed the day before the intervention begins (Day 0) and body weight will be measured on the first day of the intervention (Day 1), but participants will be given up to 3 days to begin in case there are technical difficulties with REDCap or other barriers to starting the intervention. Similarly, it is preferred that post-intervention questionnaires are completed the day after the intervention ends (Day 15), but up to 3 days will be allowed. On Day 8, the participant will provide body weight. The Day 14 24-h Food Record should be performed on Day 14, but can be completed on Day 12, 13, or 14 if there are anticipated logistical reasons why completion of the diary on Day 14 would not be possible. Post-intervention exit interviews will be performed with a member of the study team within one week of completing the intervention. Participants will be asked to complete the daily diaries every day at the end of the day.

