9.1.2 Hunger and hunger-related symptoms due to the intervention

For most participants, eating within only a 10-h window will mean re-adjusting their typical eating pattern. Many participants will need to rearrange their meal times—either delay breakfast or eat dinner earlier. If they delay breakfast, they might feel hungry in the few hours leading up to their eating window, especially in the first few days of the study. Similarly, they might crave something before bed if they are in the habit of eating before bed. With hunger can come lack of concentration, fatigue, dizziness, irritability, and other symptoms. All participants will be encouraged to stay hydrated and to consume a snack outside of the window if symptoms become debilitating.

Probability: Moderate

Magnitude: Low to moderate

Duration: Short-term

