17.2 Statistical analysis

The primary objective of this study is to assess the feasibility of delivering a TRE intervention to cancer survivors by way of adherence. As the primary endpoint, we will determine how many days the participants were able to restrict their eating to the 10-h window. Success will be deemed if participants on average reach the fasting target at least 11 of the 14 days (79% of days). This goal is based on prior TRE studies.^{17,21} A secondary aim is retention; it is hypothesized that at least 80% (32 out of 40) of those who provide baseline data also provide post-intervention data; this goal is based on prior studies conducted by the Division of Cancer Control.

To ensure safety of this intervention, body weight will be monitored weekly from baseline to post-intervention. It is anticipated that no one will lose more than 3% body weight in one week or 5% body weight over the 14 days.

In exploratory analyses, we will assess fatigue and well-being from the FACIT-F and BFI questionnaires, as well as general symptoms from the Symptom Inventory. The distribution of the outcome measures at baseline, at 14 days, and the change score (from baseline to 14 days) will be first assessed visually (e.g., histogram) and then descriptive statistics [e.g., range, interquartile range, mean (95% confidence interval), standard deviation] will be evaluated. The magnitude of the change score together with variability and distribution data will be used to inform the sample size and design of our future study. A paired t-test will be used to formally assess whether the change over time was different from zero with a two-tailed α of 0.10. For a particular outcome measure, $n=32$ patients provides 80% power to detect changes at the magnitude of 0.45 of the measured variability estimated by the standard deviation.

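### Section 8.1 gives an assurance about fatigue over the diet period, but the planned fatigue analysis does not reach Days 1-7, and the diary ratings that do are in no planned analysis and have no pre-diet value

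*Combined protocol and SAP*

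**What the plan says.** Section 8.1, after noting that fatigue and quality-of-life information will be collected, says that "it will be ensured that the diet pattern does not cause large amounts of fatigue", and extends this to quality of life and chronic symptoms. The statement is not limited to the end of the intervention, and 'large' is not defined.

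Section 9.1.2 says that participants who delay breakfast may feel hungry, "especially in the first few days of the study", and lists fatigue and dizziness among the symptoms that can come with hunger.

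For the FACIT-F, BFI and Symptom Inventory, section 4.4 says: "Patients will complete these instruments at baseline and post-intervention". On the FACIT-F: "It captures symptoms in these categories over the last 7 days". The BFI asks about fatigue now "and the usual and worst in the last 24 h". No recall period is given for the Symptom Inventory. On timing, section 8.2.5 says "it is preferred that post-intervention questionnaires are completed the day after the intervention ends (Day 15), but up to 3 days will be allowed".

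Section 4.3 has participants complete a diary at the end of each of the 14 days, including "the time they go to bed, and their average fatigue level for the day". The schedule table (section 8.2.7) assigns the diary to the primary aim.

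In section 17.2 the exploratory analysis is described as "we will assess fatigue and well-being from the FACIT-F and BFI questionnaires, as well as general symptoms from the Symptom Inventory", at baseline, at 14 days and as change. The safety paragraph of 17.2 covers body weight only. The diary fatigue item is not named.

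**The concern.** The assurance in 8.1 covers the diet period as a whole. The analysis that would inform it looks at two time points, and the later one looks back over week 2 at most. If fatigue rises in the first days and then settles, a baseline-to-Day-15 comparison will not show it, although the first days are when the protocol itself expects hunger to be most noticeable. The participants are cancer survivors enrolled because they are already fatigued, and the change scores are to inform the size and design of the next study. Whether the first week is harder to tolerate is something a feasibility pilot should be able to report.

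The plan already collects the data that could show this, in the diary. It plans no use of them, and without a rating before the diet starts, the Day 1-7 values have nothing on the same scale to be compared with.

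**Working it through.** **Inputs.** Recall periods: FACIT-F 7 days; BFI now and last 24 h (4.4). Post-intervention questionnaires: Day 15 preferred, up to 3 days allowed (8.2.5); within 3 days of finishing the intervention (8.2.4), that is, by about Day 17. Diary: Days 1-14 (4.3). Expected attrition 20%, leaving about 32 of 40 (17.1). Paired t-test, two-tailed alpha 0.10, 80% power for 0.45 SD with n = 32 (17.2).

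**1. The plan's own figure.** Noncentrality = 0.45 × √32 = 2.546; critical value t(0.95; 31 df) = 1.696; power from the noncentral t = 80.1%. The effect detectable with exactly 80% power is 0.449 SD, and 32 / (1 − 0.20) = 40. The stated power reproduces, and this point does not affect it. The question is which days the change score refers to.

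**2. Days covered.** For completion on day D, count the full intervention days within the recall period: D−7 to D−1 for the FACIT-F, D−1 for the BFI 24-hour items.

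| Completed on | FACIT-F covers | Days of 14 | Of Days 1-7 | BFI 24-h items cover |
|---|---|---|---|---|
| Day 15 | 8-14 | 7 | 0 | Day 14 |
| Day 16 | 9-14 | 6 | 0 | none |
| Day 17 | 10-14 | 5 | 0 | none |
| Day 18 | 11-14 | 4 | 0 | none |

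Day 18 applies only if the 3 days are counted from Day 15. If the FACIT-F's 7 days include the day of completion, each count falls by one. At best, 7/14 = 50% of the diet days are covered, and none of Days 1-7 in any case. The diary covers 14/14.

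**3. What each comparison would show.** Suppose true fatigue is b before the diet, b + δ on Days 1-7 and b again on Days 8-14, and participants answer strictly within the recall period.
- FACIT-F and BFI change, baseline to Day 15: b − b = 0, whatever δ is.
- Diary, mean of Days 1-7 minus Day 0: (b + δ) − b = δ. This needs a Day 0 rating, which is not collected.
- Diary, mean of Days 8-14 minus Day 0: 0.

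This pattern is hypothetical. The documents give no estimate of δ.

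**4. How noisy a one-day baseline is.** The documents give no day-to-day SD for the diary item, so call it s and assume independent days. The variance of a 7-day mean minus one day is s²/7 + s² = 8s²/7, an SD of 1.07s for one participant. Averaged over 32 participants, day-to-day noise contributes 1.07s / √32 = 0.19s to the standard error. That is usable for a group description but weak for classifying an individual. Real differences between participants come on top.

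**The case against.** Several stronger readings are tempting, and the documents do not support them.

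- *Early fatigue goes unmeasured.* It does not. The diary rates it on every diet day. The Symptom Inventory also includes fatigue, and because its recall period is not stated, it cannot be counted as missing week 1.
- *The mid-point check-in is the only other week-1 safety source.* It is not. Section 4.4 commits to monitoring all adverse events under CTCAE version 5 and names dizziness and worsening of fatigue as being of particular interest. Section 16 has the study chair review data and safety continuously. Neither is bound by a questionnaire's recall period.
- *The trial would conclude that the diet does not worsen fatigue.* No section draws that conclusion from the Day-15 change. Fatigue is exploratory and no decision rule rests on it.
- *People who leave early contribute nothing.* Section 13 uses whatever data they have provided, and section 17.4 plans multiple imputation, with pattern mixture models if data are suspected to be missing not at random. The anticipated 8 of 40 is attrition for any reason at any time; no week-1 or fatigue-related figure is given. A participant may also eat outside the window and still complete Day 15.
- *The protocol predicts a week-1 fatigue peak.* Section 9.1.2 ties the first few days to hunger and lists fatigue only as something that may accompany it.

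These points narrow the concern but do not remove it. Adverse-event reports capture what participants raise or are asked about; the scheduled inquiries are mid-way and at the end (9.1), and the mid-point contact may fall anywhere from Day 5 to Day 12 (14.3). Imputing a missing Day-15 score does not recover week-1 fatigue. Baseline BFI asks a similar question (usual fatigue over 24 hours), but the documents give no scale for the diary item, so the two cannot be assumed comparable.

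**Conclusion.** The point holds as a gap between the assurance in 8.1 and the analysis in 17.2. The two fatigue questionnaires with stated recall periods leave Days 1-7 out of the planned comparison. The diary records those days but has neither a planned analysis nor a pre-diet rating. A transient week-1 worsening could be missed in the planned fatigue results while being present in the raw diary data or the adverse-event log.

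This rests on participants keeping to the stated recall periods and on the Symptom Inventory not reaching back to week 1, which the documents leave open. Whether such a worsening is likely cannot be judged from the documents. The primary adherence endpoint, the retention target and the stated power are unaffected. It is an inexpensive improvement worth making, not a flaw that undermines the pilot.

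**What to change.** 1. Collect one diary fatigue rating on Day 0, already the preferred day for the baseline food record and questionnaires (8.2.5), using the same item and scale as Days 1-14.
2. In section 17.2, add a descriptive summary of diary fatigue by day from Day 0 to Day 14, plus the mean of Days 1-7 minus Day 0 and the mean of Days 8-14 minus Day 0. Use all available diary days, including those of participants who withdraw.
3. Read this summary together with the adverse-event data when addressing the 8.1 statement. Alternatively, limit that statement to the end of the 14 days, which needs no new data.

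The cost is one further entry of about a minute per participant and one descriptive table. A single Day 0 rating is a noisy baseline, and both weekly differences share it, so the results should be presented as group description. With a single arm, any change from Day 0 cannot be attributed to the diet alone.
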